9.2 SAMPLE SIZE DETERMINATION

Aim 1: There is no preliminary data for effect size estimation using the paradigm and patient population suggested in this study. The primary outcome measure in aim 1 is change in FTM.

H_0 : Mean change in Frontal midline theta power on electroencephalogram after iTBS to the medial prefrontal cortex will be equal to FMT changes after dorsolateral prefrontal cortex stimulation and stimulation of S1.

H_1 : Mean change in Frontal midline theta power on electroencephalogram after iTBS to the medial prefrontal cortex will be greater than FMT changes after dorsolateral prefrontal cortex stimulation and stimulation of S1.

I expect a medium effect size of $f^2 \geq 0.15$. With significance level set at $\alpha = 0.05$, using linear multiple regression modeling in G*Power software, with 3 predictors, an N of 45 subjects yields power of 0.82 for this crossover design. In a published study examining theta power using EEG plus iTBS at the dorsolateral prefrontal cortex in healthy adults, they found significant changes in theta power after iTBS with an N of 10 subjects⁵⁹. Therefore we propose 48 subjects for this current study, which should sufficiently power our study for the primary outcome measures.

Aim 2: Though there is no preliminary data for theta band power correlates of depression or autonomic symptoms in Parkinson's disease, there are studies that have looked at EEG spectral power correlations of cognitive symptoms in PD. In one study that contained sufficient published data to calculate power, they found a correlation between EEG spectral power and executive dysfunction in PD with an OR of 0.130 (95% CI [0.02-0.83])⁶⁰. The primary outcome measure in Aim 2a and Aim 2b is FTM. I used G*Power software to calculate sample size for a linear regression model with a significance level set at $\alpha = 0.05$ and Power = 0.80, which yielded a necessary sample size of 22 subjects. 45 subjects yields a power of 0.98 (95% confidence interval [0.24 – 0.99]). We will propose to recruit 48 subjects to ensure that our study is sufficiently powered.

Aim 2a:

H_0 : There is zero correlation between severity of autonomic dysfunction symptoms at baseline before stimulation with frontal midline theta power at baseline on electroencephalogram.

H_1 : There is a negative correlation between severity of autonomic dysfunction symptoms at baseline before stimulation with frontal midline theta power at baseline on electroencephalogram.

Aim 2b:

H_0 : There is no correlation between severity of depression symptoms at baseline before stimulation with frontal midline theta power on electroencephalogram at baseline.

H_1 : There is negative correlation between depression symptoms at baseline before stimulation with frontal midline theta power on electroencephalogram at baseline.

Exploratory objectives: There are no controlled studies using TMS or iTBS to treat autonomic symptoms. I used a meta-analysis of iTBS used to treat depression to estimate effect size⁶¹. They found a Hegdal g of 1.0 (95% CI [0.3-1.7]) for improvement in depression symptoms after iTBS. The primary outcome measure in Aim 3 is change in SCOPA-AUT and OHQ, and the primary outcome measure in Aim 4 is change in BDI-II after stimulation. Using G*Power software to calculate sample size for a multiple linear regression with 2 predictors, with $\alpha = 0.05$ and $N=45$, which yields a power of 0.95 (95% CI [0.26-1.00]). We propose to recruit 48 subjects.

Aim 3:

H_0 : Change in SCOPA-AUT and OHQ will be zero one day after stimulation and 4 days after stimulation compared to pre-stimulation.

H_1 : Change in SCOPA-AUT and OHQ will be less than zero one day after stimulation and 4 days after stimulation.

Aim 4:

H_0 : Change in BDI-II will be zero one day after stimulation and 4 days after stimulation compared to pre-stimulation.

H_1 : Change in BDI-II will be less than zero one day after stimulation and 4 days after stimulation.

Therefore, we propose 48 subjects for this current study which should anticipate adequate levels of power for hypothesis testing of parameters defined based on the primary outcome variables. To recruit 48 participants, based on our recruitment for prior studies with similar patient population at UNC, we anticipate pre-screening 400 potential participants' charts. We anticipate then screening 90 potential participants to find 48 participants who fulfill inclusion and exclusion criteria and who are interested in participating in the study, and are reasonably expected to be able to complete the study protocol.

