3 OBJECTIVES AND OUTCOME MEASURES

OBJECTIVES	Outcome Measures

Primary
 
Aim 1: To determine whether iTBS to the medial prefrontal cortex (mPFC) produces more robust changes in frontal midline theta (FMT) EEG power in people with Parkinson's disease compared with stimulation at the dorsolateral prefrontal cortex (DLPFC) or the primary sensory cortex (S1). Aim 2: A. To evaluate FMT power correlations with burden of autonomic symptoms at baseline before stimulation in Parkinson's disease. B. To evaluate FMT power correlations with burden of depression symptoms at baseline before stimulation in Parkinson's disease
	
Aim 1: Degree of change of frontal midline theta power on EEG after brain stimulation. Aim 2: Degree of association between autonomic symptoms and frontal midline theta EEG power; Degree of association between depression symptoms and frontal midline theta EEG power.

Exploratory
 
Aim 3: To evaluate the effect of iTBS on autonomic symptoms one day after, and 4 days after stimulation. Aim 4: To evaluate the effect of iTBS on depression symptoms one day after, and 4 days after stimulation.
 
Aim 5: To create a database of EEG and TMS data in people with PD for
	
1. Change in SCOPA-AUT and OHQ from before to after iTBS; 2. Change in BDI-II from before to after iTBS

OBJECTIVES	Outcome Measures
the purpose of future research into novel neurostimulation therapies for PD NMS	

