9.1 STATISTICAL HYPOTHESES

Aim 1

H_0 : Mean change in Frontal midline theta power on electroencephalogram after iTBS to the medial prefrontal cortex will be equal to FMT changes after dorsolateral prefrontal cortex stimulation and stimulation of S1.

H_1 : Mean change in Frontal midline theta power on electroencephalogram after iTBS to the medial prefrontal cortex will be greater than FMT changes after dorsolateral prefrontal cortex stimulation and stimulation of S1.

Primary Outcome Measure: The primary objective will test the degree of change in frontal midline theta (FMT) power (μ) before and after iTBS at each stimulation location. The primary outcome measure will be FMT power. *Aim 2a Hypothesis:*

H_0 : There is zero correlation between severity of autonomic dysfunction symptoms at baseline before stimulation with frontal midline theta power at baseline on electroencephalogram.

H_1 : There is a negative correlation between severity of autonomic dysfunction symptoms at baseline before stimulation with frontal midline theta power at baseline on electroencephalogram.

Aim 2b Hypothesis:

H_0 : There is no correlation between severity of depression symptoms at baseline before stimulation with frontal midline theta power on electroencephalogram at baseline.

H_1 : There is negative correlation between depression symptoms at baseline before stimulation with frontal midline theta power on electroencephalogram at baseline.

- Primary Outcome Measures: We will test associations between autonomic symptoms, depression symptoms, and FMT power at baseline before stimulation, where the FMT power (μ) will be the primary outcome measure.

Exploratory objectives

Aim 3 Hypothesis:

H_0 : Change in SCOPA-AUT and OHQ will be zero one day after stimulation and 4 days after stimulation compared to pre-stimulation.

H_1 : Change in SCOPA-AUT and OHQ will be less than zero one day after stimulation and 4 days after stimulation.

- Primary Outcome Measures: Change in SCOPA-AUT and OHQ from before to one day and 4 days after stimulation

Aim 4 Hypothesis:

H_0 : Change in BDI-II will be zero one day after stimulation and 4 days after stimulation compared to pre-stimulation.

H_1 : Change in BDI-II will be less than zero one day after stimulation and 4 days after stimulation.

- Primary Outcome Measure: Change in BDI-II before to one day and 4 days after stimulation

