9.4 STATISTICAL ANALYSES

9.4.1 GENERAL APPROACH

All data are double entered by independent keyboard operators, compared to identify discrepancies, then reconciled with the data manager. All datasets are backed up daily. Linear mixed models with repeated measures across different regions or over time will be the primary analytic tool for testing our *a priori* hypotheses. To model correlation among repeated measures, we will primarily consider either random intercept or AR(1). We will use the likelihood ratio test (or Wald test) statistic to test

the hypotheses. We will appropriately handle missing data (e.g., missing responses and/or covariates) by using imputation or other methods. To identify significant component terms in each of the models, we will examine the parameter estimates, 95% confidence intervals, and p-values of the component terms in an analysis of fixed effects for the final mixed models. Before undertaking statistical modeling, we will perform descriptive analyses and examine the distributions of all measures. Appropriate transformations or nonparametric statistical tests will be considered if necessary. **All statistical estimates of population parameters will be tabulated along with corresponding confidence intervals (CIs) and/or standard errors (SEs) to convey levels of precision / imprecision.** Following is a detailed plan for testing each hypothesis and the power assessment when feasible.

Descriptive statistics: Categorical data (sex) will be presented as percentages. Continuous data (age, disease duration, scores on SCOPA-AUT, OHQ, BDI-II, MDS-UPDRS all parts, freezing of gait questionnaire, Epworth Sleepiness scale, REM sleep behavior disorder questionnaire, and MoCA, will be presented as means with standard deviation and range.

Primary analysis, Aim 1: To test the degree of change in the power of FMT before and after iTBS at each location, we will use linear mixed models with FMT being the dependent variable. We will primarily include stimulation location (mPFC, DLPFC, S1), time (before, after stimulation), and the interaction term Location*time in the model.

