Primary Analysis, Aim 2: 1. To test associations of autonomic symptoms in PD subjects with FMT, we will use linear regression modeling. The dependent variable will be FMT, whereas primary covariates will be SCOPA-AUT, OHQ score, and magnitude of systolic blood pressure reduction during orthostatic blood pressure measurement. We will further use linear regression models to examine the associations between depression symptoms in PD subjects and FMT, using linear regression modeling. **Exploratory Analyses:** 1. We will use linear mixed models to examine the effect of iTBS on autonomic symptoms one day after, and 4 days after stimulation. SCOPA-AUT and OHQ will be the dependent variable in the ANOVA analysis. The factors will be stimulation location (mPFC, DLPFC, S1) by time (before and after). 2. Similarly, we will use linear mixed models to evaluate the effect of iTBS on depression symptoms one day after, and 4 days after stimulation. BDI-II will be the dependent variable, whereas the primary factors will be stimulation location (mPFC, DLPFC, S1) by time (before and after). **In all statistical models,** Some key confounding factors (age, disease duration) will be controlled in both linear mixed effects and regression models. **Post-hoc analysis** will be performed using Tukey's method to control for multiple comparisons.

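### The Aim 1 power of 0.82 fits one one-tailed comparison only: it does not cover the stated H1, and the plan does not say which test, or how many sides, decides Aim 1

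*Combined protocol and SAP*

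**What the plan says.** **Power, Aim 1 (Section 9.2).** The effect is assumed, because no preliminary data exist: f2 of at least 0.15, alpha 0.05. The text continues that "using linear multiple regression modeling in G*Power software, with 3 predictors, an N of 45 subjects yields power of 0.82 for this crossover design". It names neither the G*Power sub-procedure nor the number of tails. It then proposes 48 subjects, "which should sufficiently power our study for the primary outcome measures".

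**Hypothesis, Aim 1 (Sections 4.1, 9.1, 9.2).** Under H1 the mean change in FMT power after mPFC stimulation "will be greater than FMT changes after dorsolateral prefrontal cortex stimulation and stimulation of S1". This is directional and has two comparators. The Aim 1 objective (Sections 1.1, 3 and 4.1) joins the same two comparators with *or*.

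**Analysis, Aim 1 (Section 9.4.1).** A linear mixed model for FMT is planned: "We will primarily include stimulation location (mPFC, DLPFC, S1), time (before, after stimulation), and the interaction term Location*time in the model". On testing: "We will use the likelihood ratio test (or Wald test) statistic to test" the hypotheses. Estimates, confidence intervals and p-values of the component terms will be examined, age and disease duration are controlled, and post-hoc comparisons use Tukey's method.

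**Aim 2.** Section 9.2 starts from an odds ratio of 0.130 (95% limits 0.02 and 0.83). It reports a required N of 22 for 80% power, and power 0.98 at N = 45 with an interval of 0.24 to 0.99. In Section 9.4.1 the "primary covariates will be SCOPA-AUT, OHQ score, and magnitude of systolic blood pressure reduction during orthostatic blood pressure measurement".

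**The concern.** Section 9.2 presents 0.82 as the power of the crossover and uses it to conclude that 48 subjects are enough for the primary outcomes. A multiple regression in 45 subjects has one record per person. The crossover yields six FMT values per person (three sites, before and after).

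The planned interaction has (3 - 1) x (2 - 1) = 2 df, and a 2-df likelihood-ratio or Wald test has no direction. H1 is directional and asks for superiority over two sites. Tukey-adjusted pairwise comparisons are a third possibility. These tests differ in power and in multiplicity, and the plan does not say which decides Aim 1.

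Two things are at stake. A null Aim 1 result cannot be read against a power figure whose test is unidentified. And if the contrast and the number of sides are not fixed in advance, they can be chosen after the data are seen.

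**Working it through.** **1. Reproduce 0.82.** Inputs from Section 9.2: f2 = 0.15, alpha = 0.05, p = 3 predictors, N = 45. Residual df = 45 - 3 - 1 = 41. Noncentrality: lambda = f2 x N = 0.15 x 45 = 6.75 for F, and sqrt(6.75) = 2.598 for t.

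| Test in the same regression | N = 45 | N = 48 |
|---|---|---|
| One coefficient, one-tailed t | **0.819** | 0.841 |
| One coefficient, two-tailed t | 0.718 | 0.747 |
| 2-df F | 0.604 | 0.637 |
| 3-df F (all three predictors) | 0.528 | 0.561 |

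Only the first row gives 0.82. Adding age and disease duration (p = 5) leaves it at 0.818. The exploratory figures in Section 9.2 show the same pattern: 0.95 and 0.26 reproduce one-tailed (0.951 and 0.256) but not two-tailed (0.906 and 0.166), taking f2 = (g/2)^2 with 2 predictors. That conversion is also inferred.

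**2. A crossover reading that also gives 0.82.** Take one contrast of pre-to-post changes per person, with standardised effect dz = sqrt(0.15) = 0.387. The noncentrality is 0.387 x sqrt(45) = 2.598 on 44 df. Power is 0.819 one-sided and 0.719 two-sided. So 0.82 fits one one-sided paired contrast, but not two.

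**3. Illustration for the full H1.** Assumptions, none from the documents: dz = 0.387 for both mPFC - DLPFC and mPFC - S1, correlation 0.5 between the contrasts, pooled error on 2(N - 1) df, each contrast tested at 0.05, 1,000,000 simulated draws.

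| Both contrasts must succeed | N = 45 | N = 48 | Correlation 0.3 to 0.7, N = 45 |
|---|---|---|---|
| One-sided | 0.72 | 0.75 | 0.70 to 0.75 |
| Two-sided | 0.60 | 0.63 | 0.57 to 0.63 |

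With separate variances per contrast the N = 45 values are 0.71 and 0.58.

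Other rules at N = 45 under the same assumptions:
- 2-df interaction, lambda = (4/3) x 45 x 0.15 = 9.0: 0.76.
- One Tukey-adjusted contrast: about 0.59.
- mPFC against the mean of the other two sites: 0.91 one-sided, 0.84 two-sided.

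If f = 0.387 is instead a three-level within-person effect on change scores, lambda = 3 x 45 x 0.15 = 20.25 and the interaction has power 0.98.

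**4. Aim 2.** Section 9.2 gives no conversion from odds ratio to f2. I infer d = ln(OR) x sqrt(3)/pi, r = d/sqrt(d^2 + 4), f2 = r^2/(1 - r^2), which equals d^2/4.

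- OR 0.13: d = -1.125, r = -0.490, f2 = 0.316. One-tailed power for one coefficient is 0.799 at N = 21, 0.817 at N = 22 and 0.981 at N = 45. This reproduces both 22 and 0.98.
- OR 0.83: r = -0.051, f2 = 0.0026. Power at N = 45 is 0.096 one-tailed and 0.063 two-tailed. Stated: 0.24.
- OR 0.02: power at N = 45 is 1.00. Stated: 0.99.

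Neither stated limit is returned. At OR 0.13 and N = 45, power is 0.96 two-tailed and 0.87 for a joint 3-df test of the three autonomic covariates. The N for 80% power is 27 and 39 respectively, both below 45.

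**The case against.** The best defence is that a single-coefficient calculation is not foreign to the plan. Section 9.4.1 says that component terms will be examined, a Wald test can have 1 df, and the three predictors may be location, time and their interaction. H1 is directional, so a one-sided test is arguable, and one one-sided paired contrast with dz = 0.387 has exactly the stated power. This stands in part. Because the deciding test is unnamed, one cannot say flatly that 0.82 is the power of the wrong test. But none of this text selects a contrast or a side, and one contrast is not an H1 with two comparators.

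Three stronger readings are tempting, and the documents do not support them:

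- *The trial is underpowered.* No within-person SD or correlation is given, f2 = 0.15 is a stated lower bound, and some readings give power above 0.90.
- *The objective and the hypotheses set two different targets.* The *or* in the objective can be read as exceeding each comparator. H0 and H1 use *and* consistently. This is loose wording to align.
- *The Aim 2 lower limit should be 0.10, and 0.24 is an entry slip.* Entering 0.02 directly as f2 does give 0.239, but entering 0.83 the same way gives 1.00, not 0.99. The conversion is inferred and does not return 0.99 either.

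It is also fair that this is a pilot study with an openly assumed effect size. Section 9.2 nevertheless claims sufficient power for the primary outcomes, so the basis should be identifiable.

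**Conclusion.** The point holds as a mismatch and a missing statement. The reproduction of 0.82 rests only on inputs printed in Section 9.2 and is firm. The figure is the power of one one-tailed comparison. It does not cover H1, because the power to succeed on both contrasts cannot exceed the power on either alone. Nor does it match a 2-df Location*time test or Tukey-adjusted pairwise comparisons. One-sided testing and the deciding test are nowhere declared.

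The illustrative 0.72 and 0.60 depend on an assumed dz of 0.387 per contrast and correlation 0.5. They show how much the unstated rule matters and should not be read as the trial's true power, which the documents do not allow anyone to compute.

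For Aim 2, the conclusion at the point estimate stands on every reading checked. The interval 0.24 to 0.99 is unexplained: the conversion that reproduces 22 and 0.98 gives about 0.10 and 1.00. The term that tests Aim 2a is not named. This should be fixed; it does not call for a change in N or in the model.

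**What to change.** Keep N = 48 and the planned model.

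1. **Section 9.4.1, Aim 1.** Name the deciding test, following the formal H1. For example: *Aim 1 is decided by two contrasts of pre-to-post FMT change from the Location\*time model, mPFC minus DLPFC and mPFC minus S1, both of which must succeed, each tested [one-/two-]sided at alpha = [value]; the Tukey comparisons are [supportive only / the deciding tests].* Align the *or* in the objective (Sections 1.1, 3, 4.1) with this.
2. **Section 9.2, Aim 1.** Replace 0.82 with the power of that rule over a stated range of within-person effects and correlations. Or say that 0.82 is the power of one one-sided contrast only and not of the full H1.
3. **Aim 2.** In Section 9.2, state the odds-ratio-to-f2 conversion and the number of tails, and explain or correct the interval 0.24 to 0.99. In Section 9.4.1, say whether Aim 2a is decided by one named covariate or by a joint test of the three.

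The cost is a few sentences in two sections. No patients are added. The stated power may become less favourable. The wording should be settled before FMT results by stimulation site are examined.

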1 PROTOCOL SUMMARY

1.1 SYNOPSIS

Title:	Investigating Central Neurophysiologic Correlates of Non-motor Symptoms of Parkinson's Disease
Study Description:	This is a randomized, single-blinded, triple crossover study with 3 one-day iTBS, separated by a wash-out period of 3 weeks ¹ , sufficient for physiologic effects of one session of iTBS to return to baseline. Participants will undergo accelerated iTBS to 3 brain regions: medial prefrontal cortex (mPFC) (experimental site), dorsolateral prefrontal cortex (DLPFC) (alternative experimental site), or primary sensory cortex (S1) (control site). Participants will complete symptom questionnaires, neurologic examination and cognitive assessments, and orthostatic vital signs recording before and after each brain stimulation session.
Objectives:	

Primary Objective: Aim 1: To determine whether iTBS to the medial prefrontal cortex (mPFC) produces more robust changes in frontal midline theta (FMT) EEG power in people with Parkinson's disease compared with stimulation at the dorsolateral prefrontal cortex (DLPFC) or the primary sensory cortex (S1). Aim 2: A. To evaluate FMT power correlations with burden of autonomic symptoms in Parkinson's

disease. B. To evaluate FMT power correlations with burden of depression symptoms in Parkinson's disease

Exploratory Objectives:

Aim 3: To evaluate the effect of iTBS on autonomic symptoms one day after, and 4 days after stimulation. Aim 4: To evaluate the effect of iTBS on depression symptoms one day after, and 4 days after stimulation.

Aim 5: To create a database of EEG and TMS data in people with PD for the purpose of future research into novel neurostimulation therapies for PD NMS

Outcome measures:

Primary Outcome Measures: Aim 1: Degree of change of frontal midline theta power on EEG after brain stimulation. Aim 2: Degree of association between autonomic symptoms and frontal midline theta EEG power; Degree of association between depression symptoms and frontal midline theta EEG power.

Exploratory Outcome measures: Aim 3: Change in SCOPA-AUT and OHQ from before to after iTBS; Aim 4: Change in BDI-II from before to after iTBS

Study Population:

Study population will be men and women of all demographic groups with Parkinson's disease age 50-90 years who do not have a diagnosis of severe dementia who reside in North Carolina.

Phase:

N/A (pilot study)

Description of

UNC Medical Center will be the only participating site.

Sites/Facilities Enrolling

Participants:

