4.2 SCIENTIFIC RATIONALE FOR STUDY DESIGN

The stimulation locations in the current study design were chosen due to prior data implicating the medial prefrontal cortex and dorsolateral prefrontal cortex in both autonomic and affective disorders. Primary sensory cortex was chosen as a control site due to its limited involvement in Parkinson's disease pathology, autonomic function, and depression. We chose a control stimulation location rather than sham stimulation because participants will be able to feel the difference between real and sham stimulation in this crossover design. A triple crossover design was chosen to maximize study recruitment and minimize subject variability between stimulation arms.

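### The 0.82 power stated for Aim 1 is for one one-sided contrast, but H1 needs mPFC to exceed both DLPFC and S1; joint power is nearer 0.72 to 0.75, and the DLPFC study cited cannot support the mPFC-minus-DLPFC difference

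*Combined protocol and SAP*

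**What the plan says.** Section 9.2 states that no preliminary data exist for this paradigm and population. It assumes a medium effect, f² of at least 0.15, and reports from a G*Power multiple regression with 3 predictors and alpha 0.05 that "an N of 45 subjects yields power of 0.82 for this crossover design". It does not state the sidedness of the test or which site contrast the f² describes.

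The next sentence turns to a single piece of earlier work, described as "examining theta power using EEG plus iTBS at the dorsolateral prefrontal cortex in healthy adults, they found significant changes in theta power after iTBS"; its sample was 10. The paragraph then concludes: "Therefore we propose 48 subjects for this current study, which should sufficiently power our study for the primary outcome measures".

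The alternative hypothesis, in 9.1 and again just above the power statement in 9.2, is that the mean change after mPFC stimulation "will be greater than FMT changes after dorsolateral prefrontal cortex stimulation and stimulation of S1". The synopsis gives the two comparators different roles: "dorsolateral prefrontal cortex (DLPFC) (alternative experimental site), or primary sensory cortex (S1) (control site"). Section 4.2 says the stimulation sites were chosen on "prior data implicating the medial prefrontal cortex and dorsolateral prefrontal cortex in both autonomic and affective disorders", and that S1 is the control because of its limited involvement.

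The planned analysis (9.4.1) is a linear mixed model with location, time and their interaction. Post-hoc comparisons use Tukey's method.

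**The concern.** There are two gaps between the power statement and the hypothesis beneath which it stands.

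First, H1 as written joins two comparisons, and one power figure is given. If that figure describes a single contrast, it overstates the chance of establishing H1, because both contrasts must succeed.

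Second, the only empirical support offered for the Aim 1 sample size is a change within the DLPFC site in healthy adults. DLPFC is a comparator in H1. A change at that site carries no information on how far mPFC exceeds it. If the DLPFC effect carries over to this population in the same direction as the mPFC effect, it makes the required difference smaller.

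The trial could therefore miss the joint H1 on the DLPFC comparison although mPFC clearly beats S1, while readers of 9.2 believe the whole primary hypothesis had 82% power.

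**Working it through.** **Inputs from 9.2:** f² = 0.15, alpha = 0.05, 3 predictors, N = 45 for the calculation and 48 planned. **Not in the documents:** the sidedness of the test, the contrast that f² describes, the SD of the theta change, the within-subject correlation, and the expected mPFC-minus-DLPFC difference.

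**Step 1. Reproduce 0.82.** With G*Power's definitions, the residual df are N − 3 − 1 = 41, and the noncentrality of a single-coefficient t test is √(f²·N) = √(0.15 × 45) = √6.75 = 2.598. For the F tests it is f²·N = 6.75.

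| Test at N = 45 | Power |
|---|---|
| One coefficient, one-sided t, 41 df | 0.819 |
| One coefficient, two-sided t, 41 df | 0.718 |
| 2 of 3 predictors, F(2, 41) | 0.604 |
| All 3 predictors, F(3, 41) | 0.528 |

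Only the first matches 0.82. The DLPFC study supplies no input to it.

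**Step 2. Correlation of the two contrasts.** Let the theta changes at the three sites have common variance σ² and common within-subject correlation ρ, as a random-intercept model (one of the two structures named in 9.4.1) implies. Then:

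- Var(mPFC − DLPFC) = Var(mPFC − S1) = 2σ²(1 − ρ)
- Cov(mPFC − DLPFC, mPFC − S1) = σ² − ρσ² − ρσ² + ρσ² = σ²(1 − ρ)
- Correlation = σ²(1 − ρ) / [2σ²(1 − ρ)] = 0.5, whatever ρ is.

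**Step 3. Power to show both halves of H1, with f² = 0.15 for each.** The two t statistics were simulated with correlation 0.5, a shared error variance and N − 4 df. Both had to exceed the critical value in the hypothesised direction.

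| N | Joint, one-sided | Joint, two-sided |
|---|---|---|
| 45 | about 0.72 | about 0.58 |
| 48 | about 0.75 | about 0.62 |

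This loss comes from requiring both contrasts and assumes nothing about DLPFC being active.

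**Step 4. Sensitivity to a DLPFC effect.** Assumption: f² = 0.15 is the mPFC-versus-S1 effect, and DLPFC produces a share s of it in the same direction. The noncentrality for mPFC versus DLPFC becomes 2.598 × (1 − s) at N = 45, so its f² becomes 0.15 × (1 − s)². For s = 25% that is 0.15 × 0.5625 = 0.084; for s = 50% it is 0.15 × 0.25 = 0.0375.

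| Share s (N = 45) | mPFC vs DLPFC, one-sided | mPFC vs DLPFC, two-sided | Joint H1, one-sided | Joint H1, two-sided |
|---|---|---|---|---|
| 0% | 0.82 | 0.72 | 0.72 | 0.58 |
| 25% | 0.61 | 0.48 | 0.55 | 0.41 |
| 50% | 0.36 | 0.25 | 0.34 | 0.23 |

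At N = 48, one-sided, mPFC versus DLPFC has power 0.84, 0.63 and 0.37 at the same shares; the joint figures are about 0.75, 0.58 and 0.36.

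None of these figures includes Tukey adjustment, which would lower them. All use the plan's own regression test, not the planned mixed model.

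**The case against.** A reader might infer that, because the cited study is of DLPFC, the 0.82 is false for mPFC versus DLPFC. The documents do not support that. The 0.82 comes wholly from an assumed f², 9.2 openly says it has no preliminary data, and f² is tied to no contrast. If the mPFC-versus-DLPFC contrast really has f² = 0.15, its own one-sided power is 0.82. For that contrast alone the figure is unsupported, not shown to be wrong.

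Nor do the documents say that DLPFC is assumed to be as inert as S1, or that both prefrontal sites are expected to move frontal midline theta. Section 4.2 speaks of autonomic and affective disorders, not theta. Section 2.2 describes DLPFC as spared by Parkinson's pathology and gives mPFC particular prominence as the node that may restore theta. The protocol reports neither direction nor size for the cited study. The DLPFC share in Step 4 is therefore purely an assumption.

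Two further points have some weight. The Aim 1 objective joins the comparators with 'or', while the hypotheses join them with 'and'; the joint figures follow the hypotheses. Also, 9.4.1 promises Tukey comparisons and tabulated estimates with confidence intervals and/or standard errors, so an mPFC-versus-S1 effect would probably be visible even if the DLPFC comparison failed. That limits the harm in reporting but does not correct the power statement.

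Finally, the sensitivity figures do not come from the planned model. That is a reason to recompute them before they enter the protocol. It does not justify leaving 0.82 as the power for H1.

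**Conclusion.** The point stands in a limited form. The stated 0.82 is the power of one one-sided contrast and is not the power for H1 as written in 9.1 and 9.2. With f² = 0.15 granted for both contrasts, joint power is about 0.72 at N = 45 and 0.75 at N = 48, a shortfall of about 10 points at N = 45 (0.82 − 0.72). This rests on one-sided tests, a contrast correlation of 0.5 and no Tukey adjustment.

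Separately, the DLPFC study gives no support for the size of an mPFC-minus-DLPFC difference. How much power that comparison has cannot be settled from the documents. Same-direction shares of 25% and 50% illustrate how quickly it falls, but nothing shows that either share applies. The correction is worth making because it is cheap and concerns a stated figure for the primary aim. It does not call the sample size of 48 into question.

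**What to change.** In 9.2:

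- State which single contrast, and which sidedness, the 0.82 describes.
- Give power for the joint H1, and for mPFC versus DLPFC as a range over an assumed DLPFC effect. Compute both for the planned mixed-model contrasts with the intended multiplicity adjustment, and state the assumed difference, SD and within-subject correlation.
- Stop using the DLPFC study as support for N on the mPFC-versus-DLPFC comparison. Note instead that DLPFC may be an active comparator.

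In 9.4.1, commit to reporting the mPFC-minus-S1 and mPFC-minus-DLPFC estimates separately, each with a confidence interval.

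Whether H1 is split, or one comparison is ranked above the other, is the sponsor's choice; the correction does not depend on it.

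The cost is a short recalculation and some wording. N stays at 48 and no procedure changes. The downside is a less favourable stated power.
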